## 10.3 Populations

As usual in the observational studies, the analyses will be performed on the total sample monitored. Only subjects specifically indicated by the Steering Committee as major, irreconcilable deviation will be excluded from analysis (§ 11.1). Missing data will not be replaced. Subgroup analyses are not anticipated, however – given the exploratory nature of the study – unplanned subgroups analyses may be performed *post-hoc*, upon indications by the Steering Committee.

## 10.4 Data analysis

### 10.4.1 Demographic, prognostic and descriptive variables

All variables will be summarized with the usual descriptive techniques: categorical variables as contingency table (absolute and relative frequency); continuous variables with sampling statistics: mean, standard deviation, median, minimum, maximum. Whenever appropriate the relevant 95% confidence interval will be reported.

### 10.4.2 Primary endpoint

The primary endpoint will be analyzed at the completion of recruitment. The proportion of choices made by the attending physician will be reported as proportion with confidence interval by level. The primary analysis will test by goodness-of-fit whether the choices were random or not. The impact of demographic and prognostic factors – including the country – on the choice may be tested, if appropriate, by chi square and/or logistic regression analysis.

Unplanned *post-hoc* subgroup analyses may be performed if requested by the Steering Committee.

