Main objective of the study	
This study includes two sections:
 
 
a] a transversal section, in which the primary objective will be evaluated;
 
b] a longitudinal section, in which the secondary objectives will be evaluated.
 
 
It is assumed that the distribution of the decision taken during the transversal section (primary objective) may influence the outcomes of the longitudinal section.
 
The primary objective of the study is the evaluation of the distribution of decisions and of the reasons guiding the physician's decision on the modality to manage the secondary prevention of venous thromboembolism (VTE) in patients treated for a first-ever episode of VTE, after the initial 3-12 months of anticoagulation therapy.
 
The secondary objective is the collection of data on the course of VTE recurrence, bleeding and death risk.

Endpoints of the study	
Primary endpoint:
 
The primary endpoint is the decision taken by the attending physician at the end of the period of maintenance anticoagulation (from the end of the 3rd month to the end 12th month) initiated after the index event (maintenance anticoagulation). The maintenance anticoagulant used may or may not be the same used in the acute phase of DVT (initial 7 days); for the objectives of this study, the acute treatment is not of interest. The primary endpoint will be evaluated at the visit performed at the end of the maintenance anticoagulation.
 
Secondary endpoints
 
The distribution of reasons guiding the physician's decision on the modality to manage the secondary prevention of VTE represents a secondary endpoint.
 
The other secondary endpoints encompass the frequency of thromboembolic complications, of bleeding complications, or death from any cause monitored during the follow-up.

Number of Countries	Nine: Portugal, Poland, Czech Republic, Slovakia, Rumania, Russia, Tunisia, China, Mexico
Number of Centers	Approximately from 5 to 20 Centers in each Country. Each center shall recruit not more than 40 subjects.

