Study Procedures	
Enrollment and baseline visit:
 
 
1. the physician will assess the inclusion/exclusion criteria for entering the study and obtain the informed consent to confer the study data;
 
2. after obtaining the consent, the attending physician will record the diagnostic and prognostic information required in the CRF and inform the promoter of the recruitment of the patient;
 
3. the attending physician, based exclusively on the personal judgment and in accordance with the local procedures, will decide whether to continue with anticoagulation (NOACs or VKAs or LMWHs); or to switch to a long-term antithrombotic prophylaxis; or permanently discontinue the pharmacological prophylaxis. This decision generates three sub-populations with regards to the secondary prophylaxis of VTE: 
 
a] subjects receiving extended anticoagulation, with the same or another substance of the same class, at the same or lower dose as used in the maintenance treatment;
 
b] subjects receiving long-term antithrombotic non-anticoagulant prophylaxis;
 
c] subjects not receiving any long-term pharmacological prophylaxis.
 
 
 
4. the attending physician will record in the CRF the reasons guiding the decision taken;
 
5. the physician will instruct the subject on the procedures of the follow-up that should be the normal procedures in use at the Center, will provide a contact
 

	
reference and will obtain a contact reference.
 
Follow-up visits
 
The follow-up will be articulated as normally performed at the Center. The common follow-up procedures include a telephone contact every 3/6 months (4/8 in two years) and a direct interview at the center at least once a year (two in two years).
 
At each follow-up contact, by telephone or personal, information will be collected on:
 
 
survival at the time of contact;
 
hospitalizations occurred after the previous contact;
 
events of thromboembolic complication;
 
events of bleeding complication;
 
changes in the antithrombotic/anticoagulant therapy, if any was prescribed, including the institution of an antithrombotic/anticoagulant therapy if none had been prescribed;
 
other events that prevent the continuation of the planned follow-up.
 

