## 8.2 Study set-up

### 8.2.1 Eligibility

Approximately 3,200 subjects will be enrolled. Each center will recruit not more than 40 among the consecutive subjects coming to the observation after approval of the protocol by the relevant EC/IRB until the total planned number of cases is overall collected. Consecutiveness may be replaced by other mean of bias containment if necessary given the center operational structure (e.g., all consecutive subjects reporting each first week of the month, a definite day in the week, or similar provisions). The selected predefined modality of screening and including patients should be declared by the participant centers. The subjects shall be able and willing to issue the informed consent to confer their data. Male and female adult and elderly subjects of any ethnicity, having had a first-ever event of DVT of the lower limbs and/or PE, treated with anticoagulants according to the local procedures but for not less than 3 and not more than 12 months, and having reached the final decision point on the therapy, are eligible to enter the study.

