## 8.4 Data management

The investigators will directly manage the primary data, as usual. The responsibility to properly collect and record the data into the hospital, center or other subject's documents remains with the individual attending physicians. The responsibility to collect, verify and record possible adverse drug reactions remains with the local responsible for pharmacovigilance.

The investigator and/or specifically appointed co-investigator(s) will transfer the study data to the study database. The study data will be entered into an e-CRF, accessible from a standard personal computer with the use of standard browsers. The database will be unique and centralized, to facilitate maintaining proper database security with the usual maintenance procedures (data encryption, backups, checks of consistency and integrity, etc.). All data to be transferred will be anonymized; only the investigator and co-investigators will locally retain a log in which the correspondence between the study unique code and the subject's identification will be possible. This log will not exit the hospital, but shall be kept available for possible verifications within the frame of the quality assurance procedures (§ 8.5).

Each investigator and duly delegated co-investigator will have a personal username and password allowing access to the centralized database. All investigators at one Center can have access to the data of their center. In this context, "center" means an operating unit in which one or more investigators monitor a number of subjects, who are not seen for the same reason by other units.

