### 10.2 Sample size

The study anticipates recruiting approximately 3,200 subjects, based on considerations relevant to the primary endpoint.

The primary endpoint is the decision taken by the attending physician at the end of the maintenance anticoagulation initiated after the index event. Three options are possible: continue with extended anticoagulation (regardless of individual drug and dose), replace the anticoagulation with an antithrombotic, non-anticoagulant treatment, or stop any pharmacological prophylactic treatment.

In absence of other determinants, the null hypothesis is that the distribution of subjects by option is uniform. The analysis can therefore be performed with a goodness-of-fit test with 2 degrees of freedom. The alternative hypothesis is that at least one of the three choices is selected in a greater proportion than the other two. This analysis is performed once only at the end of recruitment.

With approximately 3,200 subjects, the study has 90% power to detect with 95% confidence a deviation from the uniform distribution, in case one of the options is selected in a proportion exceeding by 10% relative or more the proportion expected from the uniform distribution (i.e., in 36.3% or more of the subjects) [7].

Given that the factor “country” (synonymous of “healthcare system”) will be a likely cofactor in the analyses, the sample should be split across the participating countries in such a way to allow a reliable representativeness also for the smaller countries. The limit was considered not less than 100 subjects per country. The anticipated contribution by country was therefore estimated as:

Country	cases
China	approximately 200
Czechia	approximately 350
Mexico	approximately 300
Poland	approximately 900
Portugal	approximately 350
Romania	approximately 250
Russia	approximately 800
Slovakia	approximately 150
Tunisia	not less than 100

Since in this study the secondary endpoints are of clinical relevance as well, it is appropriate to estimate whether the indicated sample can yield reliable information also in relation to such endpoints.

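### The primary goodness-of-fit test, its 90% power and the intervals on the three shares make no allowance for clustering of decisions within centres

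*Combined protocol and SAP*

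**What the plan says.** Section 10.4.2 sets out the primary analysis in two sentences: "The proportion of choices made by the attending physician will be reported as proportion with confidence interval by level" and "The primary analysis will test by goodness-of-fit whether the choices were random or not". It names no method for the intervals. Country and other factors may optionally be tested against the choice by chi square or logistic regression; centre and physician are not mentioned.

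Section 10.2 bases the sample size on a 2-df goodness-of-fit test against equal thirds: "With approximately 3,200 subjects, the study has 90% power to detect with 95% confidence a deviation from the uniform distribution", for one option chosen in 36.3% or more. It contains no design effect and no ICC.

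On how the data arise, the Synopsis (Study Procedures) and section 8.3.1 say each decision is taken "based exclusively on the personal judgment and in accordance with the local procedures". Section 8.4 defines a centre as "an operating unit in which one or more investigators monitor a number of subjects". The Synopsis plans "Approximately from 5 to 20 Centers in each Country. Each center shall recruit not more than 40 subjects", and section 8.2.1 repeats the cap.

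**The concern.** The outcome is the physician's own decision. Patients in one centre share a small number of decision-makers and one set of local procedures, so their outcomes are likely to be alike, even compared with other centres in the same country. A goodness-of-fit test and a binomial interval that count each patient as an independent observation then overstate the information in the sample.

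The three shares with their intervals are the main result of the study. If the intervals ignore centre, readers will take the shares as more precise than they are. They may also take the 90% power at face value when it rests on an unstated independence assumption. No treatment or stopping decision depends on this test.

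**Working it through.** **Reproducing the plan's figure.** Take shares 0.363, 0.3185 and 0.3185 (the other two equal, an assumption), N = 3,200, alpha 0.05, 2 df.
- w² = 3 × [(0.363 − 1/3)² + 2 × (0.3185 − 1/3)²], so w = 0.0629.
- λ = 3,200 × w² = 12.67, and the power from the noncentral chi-square is 90.05%.

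The stated 90% is therefore the figure for a design effect of exactly 1.

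**Centre sizes.** The country quotas in section 10.2 sum to 3,400.
- Fewest centres: the larger of 5 and quota/40 rounded up, per country, which gives 91.
- Most centres: 20 per country, but 23 for the quota of 900 because 900/40 = 22.5, which gives 183.
- With subjects spread evenly within each country, the size-weighted mean centre size m_w = Σm²/Σm is 37.98 (91 centres) or 26.69 (183 centres).

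**Formulas.**
- DEFF = 1 + (m_w − 1) × ICC, with ICC measured within country and assumed.
- Power allowing for clustering uses λ/DEFF.
- Half-width at 36.3% = 1.96 × √(0.363 × 0.637/3,200) × √DEFF; the first part is 1.67 points.
- Coverage of a plain 95% interval = 2Φ(1.96/√DEFF) − 1.
- Rejection rate of the plain test when overall shares are equal but centres differ = P(χ²₂ > 5.991/DEFF).

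Results with no differences between countries (91 centres / 183 centres):

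| | ICC 0.01 | ICC 0.05 | ICC 0.10 |
|---|---|---|---|
| DEFF | 1.37 / 1.26 | 2.85 / 2.28 | 4.70 / 3.57 |
| Power at 36.3% | 78% / 82% | 46% / 55% | 29% / 37% |
| Half-width, points | 1.95 / 1.87 | 2.81 / 2.52 | 3.61 / 3.15 |
| Coverage of plain interval | 91% / 92% | 75% / 81% | 63% / 70% |
| Plain test rejects equal overall shares | 11% / 9% | 35% / 27% | 53% / 43% |

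80% power needs λ = 9.63, so the largest tolerable DEFF is 12.67/9.63 = 1.315. That corresponds to an ICC of at most 0.315/36.98 = 0.0085 (91 centres) or 0.315/25.69 = 0.012 (183 centres).

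**Country differences work the other way.** A plain interval counts between-country spread as sampling error, but fixed country strata remove it. Suppose one option's share is d higher in countries holding half the sample and d lower in the rest. The variance ratio (stratified clustered over plain) is then about DEFF × [1 − d²/(2/9)].
- With d = 0.20 the factor is 0.82. The ratios are 1.12 / 2.34 / 3.85 (91 centres) and 1.03 / 1.87 / 2.93 (183 centres), and coverage is 94–95% / 80–85% / 68–75%.
- The plain interval is wide enough only while ICC ≤ [d²/(2/9 − d²)]/(m_w − 1). That limit is 0.0013–0.0018 for d = 0.10 and 0.006–0.0085 for d = 0.20.

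**Simulation check** (Dirichlet-multinomial, 6,000 runs per setting). Intervals with centre as cluster and country as stratum covered 94–95% throughout. The Rao-Scott test had size 4.6–5.7%. Its power at 36.3% was 77–81% / 47–56% / 31–38% with no country differences, and 83–86% / 51–61% / 33–43% with d = 0.20.

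**The case against.** Several points on the other side are fair.

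- **The test is valid under a literal reading of its null.** If every choice is independently random, the ICC is zero and the size is correct. This stands. The rejection rates in the table belong to a different null, equal overall shares with differing centres. But section 10.2 words both its hypotheses in terms of shares, and a rejection alone does not separate unequal shares from centres that differ.
- **No plain interval is actually specified.** True: the method is omitted, so the coverage figures are conditional on plain intervals being used.
- **The ICC is unknown.** At 0.01 the half-width grows by less than 0.3 point, and with 20-point country differences the plain interval is nearly correct. The serious figures need an ICC of 0.05–0.10.
- **The power loss is shown at the boundary.** With one option at 40%, power is still at least 92% at the worst design effect of 4.70; at 42% it is at least 99% throughout. A large departure would survive correction.
- **Centres could be treated as fixed.** Between-centre variation is then not sampling error. That reading fits poorly with a plan in which "the sample should be split across the participating countries in such a way to allow a reliable representativeness also for the smaller countries", and whose section 10.1 relates the hypothesis to physicians' attitudes in general.
- **Section 10.1 calls the study exploratory.** This lowers the weight of the p-value but not of the intervals, which are the descriptive result.

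**Conclusion.** The concern holds. The test, the power statement and the intervals as written make no allowance for centre, and the plan's own account of how decisions are made renders independence doubtful. That omission is certain; the size of the harm is not, because it depends on an ICC that the documents do not supply.

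The damage ranges from slight (ICC 0.01 with wide country differences) to substantial (ICC 0.05 or more, where power at 36.3% falls to roughly 30–60% and plain 95% intervals cover 63–85%). These figures assume that participating centres stand for a wider set of centres, that the quotas are filled as listed, and that the two remaining options are equally frequent. The point should be fixed, but it does not threaten the study: a clearly unequal distribution would still be recognised.

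**What to change.** In section 10.4.2 and the matching Synopsis text:
- compute the intervals for the three shares with centre as cluster and country as stratum;
- replace the plain test with a Rao-Scott corrected goodness-of-fit test;
- report the observed ICC;
- word the conclusion as a difference from equal thirds, not as evidence on whether choices were random.

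In section 10.2, state that the 90% assumes independent decisions, and show power for a range of ICCs, for example 0.01, 0.05 and 0.10.

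The cost is plan wording and standard survey software. The e-CRF already records centre (Appendix IV, Baseline form 1/8), so no new data or subjects are needed. The price is usually wider intervals and a less favourable stated power. Where countries differ widely and the ICC is very small, the stratified interval is slightly narrower (1.5–1.6 against 1.6 points with 20-point differences and ICC 0.005). The change does not remove the bias from self-selected investigators that section 8.1.3 acknowledges.

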#### 4. Synopsis

Title of the study	WHITE Study: WHIch decision after a first venous ThromboEmbolism? [Multicenter, multinational, investigators-initiated, observational, prospective study to evaluate the decisions taken by clinicians at the end of the maintenance treatment of subjects with a first-ever event of deep vein thrombosis of the lower limbs and/or pulmonary embolism, the relevant reasons, and the attending long-term outcomes]
Code of the study	WHITE Study
Version	Final Version
Date	20 September 2017
Design of the study	international, non-profit, multicenter, observational, prospective
Promoter of the study	Fondazione Arianna Anticoagulazione, Bologna (Italy)
International Coordinator of the study	[name]
Rationale	
Patients having experienced a first-ever episode of DVT of the lower limbs and/or PE, receive anticoagulation therapy for a period as recommended by international and/or local practice guidelines. When this recommended period expires, the attending physician has to decide whether to continue with anticoagulation, switch to anti-thrombotic of another class, or stop any prophylactic pharmacological treatment. Little is known as to which proportion of subjects is assigned to each alternative, whether this proportion is equivalent across different countries, different healthcare systems, and very little is known about the reasons guiding the physician's decision.
 
After the decision is taken, a number of validated data is available in the literature regarding the outcomes in subjects assigned to extended anticoagulation for up to one year, whereas little if any information is available for subjects receiving extended anticoagulation for more than one year, or assigned to alternative long-term treatment, or who stopped the treatment.
 
The Fondazione Arianna promotes this international, investigators-initiated, multicenter observational study, to collect data that may possibly answer the first question, and give substantial indications concerning the second question.

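### The primary goodness-of-fit test can show only whether the three pooled totals are equal, not whether choices were random, and the country comparison that would help is left optional

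*Combined protocol and SAP*

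**What the plan says.** Section 10.2 sets the hypothesis: "In absence of other determinants, the null hypothesis is that the distribution of subjects by option is uniform". It continues: "The analysis can therefore be performed with a goodness-of-fit test with 2 degrees of freedom". The alternative is that at least one option is chosen more often than the other two. The sample of about 3,200 is based on this test.

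Section 10.4.2, and the synopsis in the same terms, give the test a different meaning: "The primary analysis will test by goodness-of-fit whether the choices were random or not". The same section commits to reporting each option's proportion with a confidence interval. It then says that the effect of demographic and prognostic factors, country among them, may be tested if judged appropriate. Section 10.4.3 commits to tabulating the physicians' reasons by choice.

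The synopsis rationale lists among the unknowns "whether this proportion is equivalent across different countries, different healthcare systems", and section 6.2 repeats the point for healthcare systems. Section 10.2 calls country a likely cofactor and sets a floor of 100 subjects per country. Section 10.3 anticipates no subgroup analyses. No weighting, stratification or allowance for centre is stated for the primary result.

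**The concern.** A goodness-of-fit test against one third each examines only the marginal totals. Random choice means that the decision does not depend on the patient, the centre or the country, and three pooled totals carry no information about that. Physicians who ignore every patient characteristic but favour one option would be declared not random. Physicians following strict rules whose totals happen to balance would not be.

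Pooling adds a second difficulty. The pooled proportions are averages weighted by how many subjects each country recruits, so the p-value can change with the mix while behaviour within every country stays the same. The analysis that would address dependence, decision by country and by prognostic factor, is the part the plan leaves open.

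At stake is the headline conclusion of the cross-sectional section: a finding of random or non-random choice would not be supported by the analysis behind it.

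**Working it through.** **Inputs from the documents.** Three options, 2 df, alpha 0.05, N = 3,200 and a detectable proportion of 36.3% (section 10.2). Country figures (synopsis and section 10.2): China 200, Czechia 350, Mexico 300, Poland 900, Portugal 350, Romania 250, Russia 800, Slovakia 150, Tunisia 100; sum 3,400. At most 40 subjects per centre (section 8.2.1). The documents give no expected choice proportions and no intraclass correlation, so those used below are assumptions.

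**1. The plan's own figure.** Noncentrality λ = N × Σ(pᵢ − 1/3)²/(1/3). The split of the remainder is not stated; assume it is equal, so p = (0.363, 0.3185, 0.3185). Then λ = 12.67. With critical value 5.99, power is 90.05%, and 90% power needs N = 3,195. The stated 90% at about 3,200 reproduces.

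**2. Random choice that is rejected.** Every subject is assigned by chance, with the same unequal probabilities everywhere:
- 50/30/20: λ = 3,200 × 3 × (0.1667² + 0.0333² + 0.1333²) = 448; rejection probability about 1.00.
- 40/30/30: λ = 3,200 × 3 × (0.0667² + 2 × 0.0333²) = 64; rejection probability above 99.99%.

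**3. Determined choice that is not rejected.** Each country follows one fixed rule, at the anticipated sizes:
- Option (a): China + Czechia + Mexico + Romania = 1,100
- Option (b): Poland + Slovakia + Tunisia = 1,150
- Option (c): Portugal + Russia = 1,150

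The expected count is 3,400/3 = 1,133.3 each. Chi-square = (33.3² + 16.7² + 16.7²)/1,133.3 = 1.47, p = 0.48. Country explains every decision, yet the test sees nothing.

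**4. Dependence on country mix.** Poland and Russia contribute (900 + 800)/3,400 = 50%. Take invented proportions of 43/28.5/28.5 in those two countries and 23.7/38.15/38.15 in the other seven.
- Anticipated mix, scaled to 3,200: option (a) pools to 0.5 × 43 + 0.5 × 23.7 = 33.35%, and (b) and (c) to 33.325% each. Goodness-of-fit p is about 1.0. In the same data, the country-by-decision chi-square is 134 on 16 df, p about 1e-20.
- Same proportions within each country, but nine equal-sized countries: option (a) pools to (2 × 43 + 7 × 23.7)/9 = 28.0%, and (b) and (c) to 36.0% each. Goodness-of-fit p is about 1e-9.

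The primary result reverses although no country's practice has changed. The example works only because (b) and (c) also pool to about one third each; fixing option (a) alone would not be enough for a 2-df test.

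**5. Clustering by centre.** Design effect = 1 + (m − 1) × ICC. With m = 40:
- ICC 0.01: 1 + 39 × 0.01 = 1.39
- ICC 0.10: 1 + 39 × 0.10 = 4.9

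The unadjusted test then behaves as though its critical value were 5.99/1.39 = 4.31 or 5.99/4.9 = 1.22, so its actual type I error is about 12% or 54%. With m = 20 the design effects are 1.19 and 2.9, and the error is about 8% and 36%.

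**6. Precision if estimation is primary.** The 95% half-width at a proportion of one third is 1.96 × √(2/9/n). Ignoring clustering, this is 1.6 points at 3,200, 3.1 at 900, 4.9 at 350 and 9.2 at 100. Multiplying by the square root of the design effect, the overall half-width becomes 1.9 points (design effect 1.39) to 3.6 points (4.9).

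**The case against.** The strongest reply is that the hypothesis is stated exactly in section 10.2, so a reader can see what is tested, and that section 10.1 calls all analyses descriptive and exploratory and not meant to confirm or reject hypotheses. On that view the randomness phrase is merely loose wording. The first part stands: the null is explicit and the power arithmetic is right. But the phrase is the plan's own statement of what its primary analysis will show, the test determines the sample size, and an exploratory label does not make an inference valid that the test cannot support.

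Several stronger readings are tempting, and the documents do not bear them out:
- A reader might infer that all of the study's questions are left to optional analyses. They are not: proportions with confidence intervals and tabulated reasons are committed. Only the analysis of country, demographic and prognostic factors is optional, along with formal comparison of the reasons.
- A reader might treat the country figures as quotas. They are approximate anticipated contributions, with a minimum for Tunisia. Dependence on the realised mix is the same either way, and any pooled multinational figure shares it.
- A reader might call country differences a study objective. They appear in the rationale and justification, not in the objectives or endpoints. A pooled result therefore fits the primary objective as written, and what is missing is a commitment to a comparison that the design prepares for.
- A reader might take the examples as forecasts. Their proportions are invented; they show what the test can and cannot distinguish, not what is likely.

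**Conclusion.** The point holds. The primary test addresses equality of three pooled totals, and the conclusion about randomness does not follow in either direction: rejection is near certain for random 50/30/20 choice, and p = 0.48 for choice fixed entirely by country. This needs no assumption about clustering or country mix. The pooled p-value also depends on the country mix, moving from about 1.0 to about 1e-9 in the illustration; that size rests on invented proportions. The 12% to 54% type I error rests on an assumed ICC of 0.01 to 0.10 and full centres of 40, and would be lower with smaller centres. The data remain fully usable. The fault lies in the stated interpretation and in what is committed, so the change should be made, but it does not threaten the study.

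**What to change.** 1. In section 10.4.2 and the synopsis, delete the claim about randomness and describe the goodness-of-fit test as a test of equal thirds only.
2. Make the three proportions with 95% confidence intervals the primary result, overall and by country, and state how the pooled figure is weighted.
3. Commit to the analysis of decision by country and by prognostic factors: a chi-square test for country and a multinomial logistic model, since the three options are unordered.
4. Allow for centre in the intervals and tests, for example with cluster-robust variances or a random centre effect.

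Centre is already recorded and prognostic factors are already on the case report form, so no new data are needed. The cost is revised wording, a little more analysis work and wider intervals, particularly in the smaller countries, where the half-width is about 9 points at 100 subjects even before clustering.
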